9.5. Administration and Timing of Doses

Details about infusion preparation and timing of administration are provided in the procedures manual. If a subject demonstrates an infusion reaction to the study drug, the subject may be premedicated with antihistamine (such as diphenhydramine hydrochloride, 50 mg orally or intravenously), and the infusion time may be extended for the remaining infusions. An attempt should be made to complete the infusion within 2 hours of when first started. Subjects should be

observed for approximately 1 hour following the first infusion of 400 mg in the placebo-controlled period. Subjects on dose escalation safety cohorts will be monitored post infusion as mentioned in Section 10.2.11.1.

Note: All clinical scales and specimen collections are to be performed before infusions.

9.6. Blinding

The placebo-controlled period is a double-blind study phase in which subjects and site personnel will be blinded to therapy. In order to preserve blinding, a minimal number of study personnel that support interim analyses and safety review will see the randomization table and treatment assignments before the study is complete. In the open-label period, treatment will remain blinded for up to the first 4 infusions to allow participants to dose escalate as described in Section 9.1 without unblinding subjects and site personnel to the original treatment assignment in the placebo-controlled period. After the 4-visit dose escalation period, all subjects will receive open-label solanezumab treatment and will remain blinded to the subject's original treatment assignment. In essence, all subjects are randomized at Visit 6 to early-start or delayed-start solanezumab treatment. To maintain blinding, dose reductions are not allowed during the dose escalation visits in the open-label period. If a dose reduction is desired, the dose at that visit should be withheld; when dosing is reinstated, the participant should begin unblinded dose escalation at 400 mg Q4W.

Emergency unblinding for AEs may be performed through an IWRS. This option may be used ONLY if the subject's well-being requires knowledge of the subject's treatment assignment. Any unblinding event performed via the IWRS will be recorded and reported by the IWRS.

In case of an emergency, the investigator has the sole responsibility for determining if unblinding of a subject's treatment assignment is warranted. Subject safety must always be the first consideration in making such a determination. If the investigator decides that unblinding is warranted, the investigator should make every effort to contact the Project Director prior to unblinding a subject's treatment assignment. If a subject's treatment assignment is unblinded, ATRI and Lilly must be notified immediately.

If an investigator, site personnel performing assessments, or subject is unblinded, the subject must be discontinued from the study. In cases where there is ethical reason to have the subject remain in the study, the investigator must obtain specific approval from the Project Director for the subject to continue in the study.

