informed consent	A process by which a subject voluntarily confirms his or her willingness to participate in a particular trial, after having been informed of all aspects of the trial that are relevant to the subject's decision to participate. Informed consent is documented by means of a written, signed, and dated informed consent form.
Interim analysis	An analysis of clinical study data, separated into treatment groups, that is conducted before the final reporting database is created/locked.
Investigational product	A pharmaceutical form of an active ingredient or placebo being tested or used as a reference in a clinical trial
investigator	A person responsible for the conduct of the clinical study at a study site. If a study is conducted by a team of individuals at a study site, the investigator is the responsible leader of the team and may be called the principal investigator.

ITT	intent to treat: The principle that asserts that the effect of a treatment policy can be best assessed by evaluating on the basis of the intention to treat a subject (that is, the planned treatment regimen) rather than the actual treatment given. It has the consequence that subjects allocated to a treatment group should be followed up, assessed, and analyzed as members of that group irrespective of their compliance to the planned course of treatment.
IWRS	interactive web response system
LMIIa	Logical Memory test, part IIa
LP	lumbar puncture
LS	least squares
MAC-Q	Memory Complaint Questionnaire
MCI	mild cognitive impairment
MedDRA	Medical Dictionary for Regulatory Activities
mITT	modified intent-to-treat
MMRM	mixed model repeated measures
MMSE	Mini-Mental State Examination
MRI	magnetic resonance imaging
NIA	National Institute on Aging
NCS	natural cubic spline
PACC	Preclinical Alzheimer's Cognitive Composite
PET	positron emission tomography
PHI	protected health information
PK/PD	pharmacokinetics/pharmacodynamics
P-tau	phosphorylated tau
QTcB	QT interval corrected using Bazett's formula
randomize	The process of assigning subjects to an experimental group on a random basis.
Re-screen	To screen a subject who was previously declared a screen failure for the same study.
RUI	Resource Use Inventory
RUI-B	Resource Use Inventory, Brief version
SAE	serious adverse event

SAP	statistical analysis plan

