8.4. Discontinuations

8.4.1. Discontinuation of Subjects

The criteria for enrollment must be followed explicitly. If the investigator site identifies a subject who did not meet enrollment criteria and who was inadvertently enrolled, the Project Director must be notified. If the Monitor identifies a subject who did not meet enrollment criteria and who was inadvertently enrolled, the investigator site will be notified. Inadvertently enrolled subjects may be maintained in the study and on investigational product when the Project Director agrees with the investigator that it is medically appropriate for that subject. The investigator must obtain documented approval from the Project Director to allow the inadvertently enrolled subject to continue in the study.

Subjects who do not meet entry criteria or who are excluded by exclusion criteria from screening tests and procedures should be discontinued from the study before randomization.

Subjects who exhibit any of the following conditions during the study may be discontinued from the study.

- Appearance of clinically significant new cerebral ischemic or hemorrhagic events or symptomatic ARIA-E or greater than 4 new microhemorrhages detected on the central read on follow up MRI scans will be flagged for review by the central review. Subject may be able to continue to participate in the study depending on clinical significance as determined by the Project Director, Medical Monitor, and the Site Investigator.

Note: while most cases of ARIA-E are asymptomatic, when symptoms do occur they are reported to be most commonly headache, worsening of cognitive function, alteration of consciousness, seizures, unsteadiness, and vomiting. Even when symptomatic ARIA-E is present, in most cases treatment is not required beyond discontinuation of the treatment until the symptoms are resolved. If a subject simultaneously develops more than 1 of the symptoms suggestive of ARIA-E, that is, headache, worsening of cognitive function, alteration of consciousness, seizures, unsteadiness, or vomiting, then an unscheduled MRI scan may be obtained. A single symptom suggestive of ARIA-E of sufficient severity may also warrant an MRI scan. The unscheduled MRI scan should be performed in the same manner as the currently scheduled MRI scans in the protocol, which includes sending the images for central review. For guidance, please refer to the instructions described in the relevant procedures manual.

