- Prolonged acute infusion reaction (that is, not rapidly responsive to medication such as antihistamines, nonsteroidal anti-inflammatory drugs, and/or narcotics and/or brief interruption of infusion).

Note: Acute infusion reactions may occur with any agent that causes cytokine release (for example, some monoclonal antibodies or other biological agents). Cytokine release may or may not be related to the mechanism of the infused biologic agent. Signs and symptoms usually develop during or shortly after drug infusion and generally resolve completely within 24 hours.

Signs/symptoms may include: allergic reaction/hypersensitivity (including drug fever), arthralgia, bronchospasm, cough, dizziness, dyspnea, fatigue, headache, hypertension, hypotension, myalgia, nausea, pruritus, rash, rigors/chills, sweating (diaphoresis), tachycardia, urticaria, and vomiting.

- Discontinuation of the study drug for abnormal liver tests should be considered by the investigator when a subject meet 1 of the following conditions after consultation with the medical monitor:
 - ALT or AST >8X ULN
 - ALT or AST >5X ULN for more than 2 weeks

- ALT or AST >3X ULN and total bilirubin level >2X ULN or prothrombin time >1.5X ULN
- ALT or AST >3X ULN with the appearance of fatigue, nausea, vomiting, right upper-quadrant pain or tenderness, fever, rash, and/or eosinophilia (>5%)

In addition, subjects may be discontinued from the study drug and from the study in the following circumstances, including but not limited to:

- Mean QTcB >500 msec and an absolute change >60 msec when compared with baseline (the most recent measurement made at either screening [Visit 1 through 5] or baseline [Visit 6]).
- Enrollment in any other clinical trial involving an investigational product or enrollment in any other type of medical research judged not to be scientifically or medically compatible with this study
- Investigator Decision
 - The investigator decides that the subject should be discontinued from the study.
 - If the subject, for any reason, requires treatment with another therapeutic agent that has been demonstrated to be effective for treatment of the study indication, discontinuation from the study occurs prior to introduction of the new agent.
- Subject Decision
 - The subject requests to be withdrawn from the study.
- Sponsor Decision
 - ATRI or Lilly or its designee stops the study.
- Adverse Event

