 - If the investigator and/or the subject decides that the subject should be withdrawn because of an SAE or other clinically significant AE, the investigational product is to be discontinued and appropriate measures are to be taken. ATRI or Lilly or its designee is to be alerted immediately. Refer to Safety Evaluations (Section 10.2).

Subjects who discontinue early from the investigational product and/or study early will be encouraged to have an early termination visit at the point of discontinuation, with procedures performed as shown in the Study Schedule ([Attachment 1](#)). Refer to the relevant procedures manual for further detail.

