9.8. Treatment Compliance

Because dosing occurs at study visits, subjects who attend all visits and successfully receive infusions are automatically compliant with treatment. Any infusions at which 75% or more of the infusate is given will be considered a complete infusion.

If a subject attends a visit but does not receive a complete infusion (for example, due to technical complications), every effort should be made to complete the infusion within 24 hours if possible. If less than 75% of the infusate is given, this must be recorded as an incomplete infusion on the case report form (CRF).

Missed infusions should be recorded on the CRF. Subjects who miss 3 consecutive infusions or 10 or more cumulative infusions at any time during the course of the study may be discontinued from the study. Subjects who miss 3 consecutive infusions or 10 or more cumulative infusions for medical reasons (for example, MRI findings) or other extenuating circumstances can continue in the study with the approval of a Medical Monitor and/or Project Director.

10. Outcome Measurements

Study procedures and their timing (including tolerance limits for timing) are summarized in the Study Schedule ([Attachment 1](#)).

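### Unblinding requires, and missed infusions, MRI/ARIA findings and prolonged infusion reactions permit, exit from the study rather than from drug alone, and no PACC follow-up off drug is specified

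*Protocol*

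**What the plan says.** Protocol 9.6 sets the only mandatory rule: "If an investigator, site personnel performing assessments, or subject is unblinded, the subject must be discontinued from the study". The next sentence gives an exception for ethical reasons, for which "the investigator must obtain specific approval from the Project Director for the subject to continue in the study".

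Protocol 9.8 is permissive: "Subjects who miss 3 consecutive infusions or 10 or more cumulative infusions at any time during the course of the study may be discontinued". Where the reason is medical or there are extenuating circumstances, such participants "can continue in the study with the approval of a Medical Monitor and/or Project Director".

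Protocol 8.4.1 introduces its list with "Subjects who exhibit any of the following conditions during the study may be discontinued from the study". Under it come listed MRI/ARIA findings and a prolonged acute infusion reaction. The liver-test item in the same list speaks of the drug only: "Discontinuation of the study drug for abnormal liver tests should be considered by the investigator". The items that follow, including QTcB prolongation, refer to drug and study together.

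On what happens next, 8.4.1 says: "Subjects who discontinue early from the investigational product and/or study early will be encouraged to have an early termination visit". It refers to a procedures manual for detail. A footnote to the study schedule (Attachment 1) allows that visit to be shortened, depending on when the last visit took place.

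The ITT entry in Protocol section 4 says that "subjects allocated to a treatment group should be followed up, assessed, and analyzed as members of that group irrespective of their compliance" with the planned course of treatment. Protocol 11.2.8 and SAP 7.9.1.1 define the primary analysis as a comparison of participants as randomized who have a baseline and at least one later PACC score.

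**The concern.** The ITT definition covers follow-up and assessment as well as analysis. The collection rules do not secure either. A participant who stops infusions or whose code is broken can be taken out of the study, and even one who stops drug only has nothing specified beyond a single voluntary visit. The PACC is scheduled every 24 weeks to Week 240, but no section keeps such a person on that schedule.

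Week 240 PACC can therefore go missing because of drug exposure, a safety event or a broken code. The primary spline model handles the gap under missing at random. In effect, people who left after stopping drug are represented by similar people who stayed. If benefit fades after drug is stopped, the result moves away from the as-randomized effect and towards the effect of continued treatment.

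The loss could also differ by arm. Emergency unblinding is provided for adverse events, and Protocol section 5 names ARIA and infusion-related reactions among the potential risks. A difference is possible but not shown.

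**Working it through.** **1. Triggers side by side**

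| Trigger | Section | Force | Exit from | Stated route to stay |
|---|---|---|---|---|
| Unblinding | 9.6 | mandatory | study | ethical reason, Project Director approval |
| 3 consecutive or at least 10 cumulative missed infusions | 9.8 | permitted | study | medical or extenuating reason, with approval |
| Listed MRI/ARIA findings | 8.4.1 | permitted | study | review of clinical significance; under 10.1.3.5 asymptomatic ARIA may stay on treatment |
| Prolonged acute infusion reaction | 8.4.1 | permitted | study | none stated beyond the permissive heading |
| Abnormal liver tests | 8.4.1 | to be considered | drug (in a list headed by exit from the study) | none stated |
| QTcB prolongation | 8.4.1 | permitted | drug and study | none stated |

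The object of the rule changes with the trigger, and no row ends in continued PACC assessment off drug.

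**2. What the analysis could use**

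SAP 7.2 says that continuous-time models take every post-baseline observation in the placebo-controlled phase. PACC scores collected after drug stop would enter the primary model as it stands. The obstacle is collection, not the model.

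**3. Number potentially affected**

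Protocol 11.1 gives N = 1150 and 30% attrition: 0.30 × 1150 = 345 without a Week 240 score. Neither document divides the 345 by cause, so the share due to these triggers is unknown.

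**4. Does off-drug follow-up raise power?**

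Inputs (Protocol 11.1): two-sided alpha 0.05, 1:1 allocation, detectable difference 0.532 with SD 2.85 (ADNI) or 0.570 with SD 3.08 (HABS), stated power 80%.

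Formula: power = Φ(δ / (SD × √(2/n)) − 1.96), with n per arm.

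The plan's own figure first:
- n = 575 × 0.7 = 402.5: 75.4% (ADNI), 74.7% (HABS).
- n = 575 / 1.3 = 442.3: 79.3% and 78.6%, close to 80%.

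The SAP says that sample size assumed an MMRM, which also uses partial data from dropouts. The simple formula is not the plan's method, so the 80% is not disputed.

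Now suppose that all 575 per arm are assessed (ADNI inputs) and that off-drug scores dilute the effect by an assumed amount:
- 10%: δ = 0.479, power 81.3%.
- 20%: δ = 0.426, power 71.6%.
- 30%: δ = 0.372, power 60.1%.

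Against the 75.4% for 402.5 per arm, the break-even dilution is 1 − √(402.5/575) = 1 − √0.7 = 0.163. Below about 16% power rises; above it power falls. The case for follow-up therefore rests on bias and on the question answered, not on power.

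**The case against.** The strongest reply is that the rules are softer than they look and that the SAP already deals with dropout. Much of this stands.

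- A reader might infer that all four triggers force people out. They do not: only unblinding is mandatory, and it has an exception. Missed infusions and ARIA have explicit routes to stay, and only a prolonged acute infusion reaction is listed.
- A reader might infer that no off-drug PACC will exist. The documents do not support that. Participants with long dosing gaps can be retained under 9.8, SAP 6.1 and 7.9.1.1 describe a COVID-19 interruption of dosing and assessments, and the early termination column of the schedule includes the PACC.
- A reader might infer that exits will differ by arm. Protocol section 5 reports few differences between arms in the earlier Phase 3 studies for discontinuations due to adverse events, ARIA and infusion reactions. The main placebo-controlled studies it describes used 400 mg every 4 weeks, so this does not settle the matter at the higher dose, but no difference is shown.
- The SAP plans a delta-adjusted tipping-point analysis in the solanezumab arm (7.9.1.2.2), between-arm comparisons of discontinuation by reason and over time (7.7), a cumulative-exposure model (7.9.1.2.4), and PACC by reason for discontinuation with dropout weighting in the dose model (7.15). These are real safeguards.
- The ITT entry is worded as a recommendation, the planned population is modified ITT, and the procedures manual may say more.

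What remains is that the safeguards test or describe the loss but do not prevent it. The tipping point can report the delta at which significance disappears. With little observed off-drug PACC, the promised judgement of clinical plausibility has little to rest on. Scores from the COVID-19 interruption are a weak stand-in, because people who paused for the pandemic need not resemble those who stopped for a safety event.

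**Conclusion.** The point holds as a mismatch between the data-collection rules and the as-randomized analysis that they are meant to feed. Unblinding requires exit unless an exception is approved; the other triggers permit it; and the protocol itself specifies no continued PACC assessment after drug is stopped.

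No size can be put on the bias. It depends on how many of the roughly 345 leave for these reasons, on how that splits by arm, and on how much benefit is lost off drug; the documents give none of these. It is tempting to charge all 30% attrition to drug stopping with half the benefit lost, which gives 0.532 × (1 − 0.30 × 0.5) = 0.452 against 0.532, an 18% overstatement. Neither premise is in the documents, and 0.532 is a detectable difference rather than an expected effect, so that figure should not be used.

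The conclusion rests on the protocol and SAP text, and a procedures manual that specifies off-drug PACC visits would narrow it. This is a worthwhile, inexpensive improvement rather than a fatal flaw.

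**What to change.** In Protocol 8.4.1, 9.6 and 9.8, separate stopping study drug from leaving the study for the purpose of data collection:

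- Unless consent is withdrawn, keep the participant on the existing PACC schedule to Week 240 after drug stop or unblinding.
- Record the date of drug stop or unblinding.
- Include these scores in the primary NCS model, and use the off-drug scores to inform the range of delta in the tipping-point analysis.
- Flag scores obtained after unblinding, and add a sensitivity analysis for them to the SAP.

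SAP 6.1 has the placebo-controlled period closing in December 2022, and the SAP approval is dated January 2023, so collection may already be over. In that case, report exits by trigger and arm (SAP 7.7 uses the CRF reasons, which may not separate these triggers) and state the limit on the as-randomized conclusion.

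The cost is protocol wording, site and participant time for visits already in the schedule, and a few scores obtained after unblinding. No new primary model is needed. Off-drug data may dilute the estimated effect, as shown above.

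The differing stopping triggers in 8.4.1, 9.6 and 9.8 must be reconciled by the sponsor with each other and with the ITT definition. No clinical rule is proposed here.

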9.7. Concomitant Therapy

All concomitant medication taken during the study must be recorded. Subjects will be instructed to consult the investigator or other appropriate study personnel at the site before initiation of any new medications or supplements and before changing dose of any current concomitant medications or supplements.

Prescription acetylcholinesterase inhibitors (AChEIs) and/or memantine are exclusionary during initial screening. Starting prescription AChEIs and/or memantine during the course of the study

will not be permitted without explicit permission for an exemption for medical necessity. Before a subject starts an AChEI and/or memantine or other treatments for cognitive impairment, a Medical Monitor must be contacted to determine whether or not the subject should continue in the study and whether or not clinical outcome measures should be performed. Participants who begin treatment with AChEIs and/or memantine during the placebo-controlled period will be eligible to continue in the open-label extension period.

Use of benzodiazepines for treatment on an as-needed basis for insomnia or daily dosing as anxiolytics is permitted. If they are being given chronically, use of sedatives or hypnotics should be avoided for 8 hours before administration of cognitive tests. If sedating medication is given for MRI at any visit or for any short-term use, then all cognitive assessments must be administered at least 24 hours after administration of the sedative.

Stable use of pain medications will be permitted. Short-term use of narcotics is allowable if not administered within 24 hours prior to cognitive assessments.

Other concomitant medications that affect CNS function may be given if the dose remains unchanged throughout the study. Doses of these compounds should remain constant from 6 weeks before randomization (Visit 6).

To avoid effects on cognitive measures:

- subjects should not stop receiving any medications that affect CNS function during the study,
- subjects should not add any medications that affect CNS function to the treatment regimen, and
- subjects should not change doses of medications that affect CNS function.

If unforeseen starting, stopping, or changing of stable doses of drugs that affect CNS function occurs during the study, a Medical Monitor must be contacted to determine whether or not the subject should continue in the study and whether or not outcome measures should be performed.

Anticoagulants, such as warfarin (Coumadin) and dabigatran (Pradaxa) are not permitted for subjects who undergo a LP. Starting anticoagulants during the course of the study, if deemed medically necessary, will be permitted; however, subsequent LP will not be conducted.

